### 11.6.2 Laboratory Data

The absolute values of each laboratory parameter (Hematology, Biochemistry) will be summarised at each visit along with the change from baseline to each post baseline timepoint (*Table 14.3.3.1 and 14.3.3.2*). In addition, shift tables from baseline to each post baseline timepoint will be presented (*Table 14.3.3.3 and 14.3.3.4*) to show Normal/ Abnormal Clinically Significant (CS)/ Abnormal Not Clinically Significant (NCS) results.

Laboratory data listings will be presented in two ways:

- Abnormal values (presented within the data summaries) (*Table 14.3.3.5*)

- All laboratory data (presented within the data listings)

If lab results are repeated at the same visit, the repeated result will be used in summaries (instead of the original one) provided the sample was taken within the visit window, otherwise the original result will be used. All results will be listed.

Lab results at unscheduled visits will be included in the listings but will not be summarised.

Serum pregnancy data will be listed only.

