Data Safety Monitoring Board (DSMB) - Independent Cardiovascular Safety Committee (ICVSC)	
A Data Safety Monitoring Board with expertise and experience in the management in UC will review the safety of the trial on a monthly basis until December 2019 and then quarterly from January 2020 onwards.
 
An Independent Cardiovascular Safety Committee (ICVSC), comprised of 3 cardiologists with experience from drug development, will be formed as detailed in the Charter. The ICVSC will be responsible for an on-going evaluation of cardiac adverse events of special interest (Cardiac AESIs), for treatment emergent echocardiographic findings, and for treatment emergent changes of cardiac safety biomarkers (as detailed above). The ICVSC will review cardiac adverse events on an on-going basis, meet regularly and provide recommendations to Sponsor and DSMB regarding study procedures and conduct.
		
Sample Size calculation	Not applicable / Maximum 30 subjects (i.e. ABX464-101's sample size)		
Statistical Methods	Safety:		

Study n°	ABX464-102	Clinical Phase	IIa
		Type of Study	Follow-up Study

Analysis of safety will be performed on the safety data set consisting in all subjects who received at least one dose of ABX464 in the study. The assessment of safety will be based on the frequency of adverse events (with and without regard to causality) graded according to the Common Terminology Criteria for Adverse Events "CTC-AE" (Version 5.0) and also, the review of individual values for clinical laboratory data, vital signs and ECG focusing on the detection of abnormal values and potentially clinically significant abnormalities (PCSA) determined upon investigator considerations.
 
All adverse events will be listed and the data will be tabulated by body system/organ class. Adverse event tabulations will include all treatment emergent adverse events, which will be further classified by severity, and relationship to treatment.
 
Clinical laboratory parameters, echocardiography parameters, vital signs, and ECG will be summarized by using descriptive statistics (n, mean, SD, SEM, median, minimum and maximum). Number of subjects with at least one abnormal value will be tabulated (counts and percentages) for each parameter in summary shift tables.
 
Efficacy:
 
Efficacy results will be presented descriptively; proper tests will be performed if appropriate.
			

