5.3.3. Physical Examination and Vital Signs

A routine physical examination (including body weight) will be done at each study visit. Physical examinations will cover eyes, ears, nose, throat, lungs/thorax, heart/cardiovascular system, abdomen, skin and mucosae, nervous system, lymph nodes, musculo-skeletal system, and, if applicable, others. Any new clinically relevant finding compared to baseline must be documented as adverse event.

Measurements of vital signs will be done at each visit (Blood pressure, Heart Rate, Body temperature). The subject should rest supine for at least 10 minutes prior to measurements. The measurements can be performed either in sitting or supine position of the subject. The right or left arm may be used. However, the position and the arm used for measurement should be kept constant throughout the trial for an individual subject.

The investigator should ensure that each parameter outside the normal range is assessed for clinical significance. For any deviation assessed clinically significant, the investigator has to document the change as an adverse event (AE) in the eCRF.

In addition, it is at the discretion of the investigator to document any change or trend over time in vital signs as an AE if he considers the change to be clinically significant, even if the absolute value is within the alert limit or reference range.

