9.3. Safety Analyses

Adverse events will be coded using the standard dictionary (MedDRA) down to the lower level term (LLT).

An overall summary table will be presented (Any adverse event, any treatment emergent adverse event (TEAE), any SAE, death, any grade 3 or higher adverse events from baseline to the end of Study. This analysis will be conducted on SAF population.

Two periods will be defined for TEAE:

- Any adverse event which occurs or worsens from first dosing to the last dosing day;
- Any adverse event which occurs after the last dosing day.

Adverse events will be described by primary system organ class and preferred term. Numbers and percentage of subjects, and number of occurrences of adverse event will be presented for:

- TEAE;
- Serious TEAE;
- TEAE leading to drug discontinuation;
- TEAE of grade 3 or 4;
- TEAE for which relationship with the study drug is recorded as possible or probable
- TEAE of special interest

The assessment of safety will be based on the frequency of adverse events (with and without regard to causality) graded according to the CTC-AE Classification and also, the review of individual values for clinical laboratory data, vital signs and ECG focusing on the detection of abnormal values and PCSAs [potentially clinically significant abnormalities (PCSAs) determined upon investigator considerations].

All adverse events will be listed and the data will be tabulated by body system/organ class. Adverse event tabulations will include all treatment emergent adverse events, which will be further classified by severity, and relationship to treatment.

Clinical laboratory parameters, echocardiography parameters, vital signs, and ECG will be summarized by using descriptive statistics (n, mean, SD, SEM, median, minimum and maximum). Number of subjects with at least one abnormal values will be tabulated (counts and percentages) for each parameter in summary shift tables.

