### 1.2 CHANGES FROM PROTOCOL

- The echocardiography secondary endpoints will be included in a separate report.
- Sustained clinical remission and sustained endoscopic remission/improvement will be summarized as part of the secondary endpoints.
- Observed Cases (OC) Set and Non-responder Imputation (NRI) Set are defined for populations instead of the populations defined in the protocol.
- In the definition of corticosteroid-free clinical remission (Section 11.3.1.6), time interval is changed from 12 weeks to 90 days for consistency with other Abivax studies.
- In the definition of clinical response (Section 11.3.1.6), Modified Mayo Score is used instead of Total Mayo Score for consistency with other Abivax studies.
- All efficacy variables will be summarized based on the following subgroups:
  - Patients being in clinical response at BOLS and not being in clinical response at BOLS
  - Patients previously treated with biological drugs and naive from biological drugs.
- In the Synopsis and Section 2.4 of the protocol, M24 is missing from the list of timepoints for clinical remission, clinical response, endoscopic improvement, endoscopic remission and corticosteroid-free clinical remission inconsistently with further sections. This timepoint is included in the current SAP to ensure that these secondary endpoints are analysed for all required timepoints.

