## 10 STATISTICAL METHODS

### 10.1 GENERAL PRINCIPLES

All variables will be presented descriptively.

All statistical methods will be based on the International Conference on Harmonisation (ICH) E9 document “Statistical Principles for Clinical Trials”.

Data will be summarised by treatment group (50mg ABX464 (101 study) + 50mg ABX464 (102 extension) and Placebo (101 study) + 50mg ABX464 (102 extension)). A total column showing all patients will be included for baseline, safety and efficacy summaries. Where appropriate, data will also be summarised by visit with summaries for each visit attended as scheduled and an additional summary for final (last scheduled visit or early withdrawal). The format of the summaries is defined in the shells at the end of this document.

In safety tables of continuous variables, standard descriptive statistics (Sample number n, mean, Standard Deviation (SD), Standard Error of the Mean (SEM), median, minimum and maximum) will be presented. In summary tables of continuous variables, standard descriptive statistics (n, mean, 95% confidence interval [CI], SD, median, minimum and maximum and quartiles) will be presented. The minimum and maximum statistics will be presented in summary tables to the same number of significant figures as the original data. The mean, median, SD and SEM will be presented to one more significant than the original data.

- For numeric data which includes non-numeric values (e.g. lab results reported as < 10 or >100) the following principles will be applied when summarising the data:
  - Below Limit of Quantification (BLQ) will be replaced with a value that is ½ of the lower limit of quantification (LLQ)
  - Results reported as < x will be treated in the same way as BLQ with LLQ=x
  - Otherwise SD and CI will not be calculated
  - Whenever meaningful, minimum, median and maximum will be presented based on the reported data (e.g. minimum = <10, median = 20, maximum = >100)

In summary tables of categorical variables, the number of non-missing observations by category will be presented with percentages. The number of missing observations will also be presented when non-zero. Unless otherwise specified, the denominator for each percentage will be the number of non-missing observations within the column. All percentages will be presented to one decimal place.

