### 11.6.3 Vital Signs

Body temperature, systolic blood pressure, diastolic blood pressure, heart rate and weight are collected at all visits.

The absolute values of the vital signs will be summarised at each visit by using descriptive statistics including the change from baseline to each post baseline timepoint (*Table 14.3.4*).

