### 11.6.5 Electrocardiogram

Electrocardiograms will be performed at Day 56, quarterly from M24 to M48 and at EoS visits.

The number and percentage of the patients with Normal / Abnormal NCS / Abnormal CS ECG results will be summarised for each visit (*Table 14.3.6*) along with the change from baseline to each post baseline timepoint.

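### The SAP gives no count of subjects with at least one abnormal laboratory, vital-sign or ECG value, and keeps the mandatory repeat of a failed safety sample out of the laboratory summaries

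*SAP*

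**What the plan says.** After naming laboratory, echocardiography, vital-sign and ECG data, protocol 9.3 states: "Number of subjects with at least one abnormal values will be tabulated (counts and percentages) for each parameter in summary shift tables". The synopsis repeats this. Protocol 9.3.1, which is specific to laboratory data, asks for descriptive statistics at scheduled assessments and shift tables from baseline.

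The SAP provides:
- **Laboratory (11.6.2):** by-visit descriptives (Tables 14.3.3.1 and 14.3.3.2); "In addition, shift tables from baseline to each post baseline timepoint will be presented" (Tables 14.3.3.3 and 14.3.3.4); and a listing of abnormal values (Table 14.3.3.5).
- **Vital signs (11.6.3, Table 14.3.4):** "The absolute values of the vital signs will be summarised at each visit by using descriptive statistics". There is no abnormal category, although protocol 5.3.3 says "The investigator should ensure that each parameter outside the normal range is assessed for clinical significance" and Listing 16.2.8.3 carries a Review field.
- **ECG (11.6.5, Table 14.3.6):** "The number and percentage of the patients with Normal / Abnormal NCS / Abnormal CS ECG results will be summarised for each visit".
- **In general (10.1):** by-visit output comes "with summaries for each visit attended as scheduled and an additional summary for final". That final summary is the last scheduled or withdrawal visit, not the worst value.

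SAP 1.2 lists seven changes from the protocol. The one that concerns safety output is "The echocardiography secondary endpoints will be included in a separate report".

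Protocol 2.4 and SAP 4.2 both list the incidence of specific laboratory abnormalities as a secondary endpoint. Neither gives criteria, and the SAP's list of tables has no output for it.

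On repeats, protocol 5.3.12 requires named safety samples without a result to be repeated and entered as an unscheduled visit. SAP 11.6.2 lists unscheduled laboratory results but does not summarise them. SAP 6.1 and 10.4 apply LOCF to missing continuous values in the OC Set, which serves all safety analyses.

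**The concern.** Long-term safety is the primary objective. For a four-year single-dose extension, a reader will ask how many subjects ever had an abnormal value of a given parameter. The protocol promises that figure twice. The SAP does not produce it and does not say that it has been dropped. Vital signs fare worst, because they have neither a shift table nor an abnormality count.

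The repeat rule is a separate problem. Two instructions, each clear in itself, combine so that a result the protocol insists on obtaining is kept out of the by-visit tables by rule. The analytes concerned include liver tests, lipase, troponin, CPK and NT-proBNP.

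**Working it through.** The documents state no figure on this point to reproduce, so the check compares the passages and counts.

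**1. By-visit counts do not give the any-time count.** If a_v subjects are abnormal at visit v, the number ever abnormal lies between max(a_v) and min(N, sum of a_v). N = 22 enrolled (protocol 1.3). Take one abnormal subject per visit:
- M27 to M48: 7 + 1 = 8 visits, so 1 to 8 subjects; 1/22 = 4.5%, 8/22 = 36.4%.
- ECG: D56, M24, M27 to M45 (7), M48 and EoS = 11 visits, so 1 to 11 subjects; 11/22 = 50.0%.
- Laboratory: D7 to D56 (6), M3 to M24 (22), M27 to M45 (7), M48 and EoS = 37 visits, so 1 to 22 subjects.

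These are arithmetic bounds from an assumed pattern. They show what the tables cannot tell the reader, not what will be observed.

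**2. Parameters under the repeat rule.** SAP 9.2.1 lists 12 hematology + 23 biochemistry = 35 parameters. Protocol 5.3.12 names total bilirubin, AST, ALT, alkaline phosphatase, lipase, INR/prothrombin, hs troponin, CPK and NT-proBNP: 9 of 35, counting INR/prothrombin and troponin once each, as the SAP does.

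**3. What happens to the repeat.**
- Descriptive tables (14.3.3.1, 14.3.3.2): the repeat is excluded as unscheduled. Read literally, 6.1 and 10.4 put the previous value in its place.
- Shift tables (14.3.3.3, 14.3.3.4): 10.4 imputes nothing for a three-category result, and percentages use non-missing observations, so the subject drops out at that visit.
- The same-visit repeat rule does not help, because the protocol records this repeat as unscheduled. The nearest-visit rule in SAP 3.4 does not clearly help either, because 11.6.2 excludes unscheduled results explicitly.

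Illustration for a late visit, assuming 14 subjects (the number protocol 1.2.5 gives as treated for more than 3 years at 30 November 2021): if the repeat is the only abnormal result, the shift table shows 0/13 = 0.0% instead of 1/14 = 7.1%.

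**4. Age of a carried value, if LOCF applies.**
- M30 to M48: 91 ± (14 + 14) = 63 to 119 days.
- NT-proBNP, M42 to M48: 183 ± 28 = 155 to 211 days.
- M27: depends on how M24 is counted. In calendar months the gap is about 91 days before windows. With the 28-day steps of protocol 5.2.3, M24 falls at 24 × 28 = day 672 and M27 at about day 822, a gap of about 150 days.
- EoS for completers: the last dose is the day before M48, so EoS is nominally 28 − 1 = 27 days after M48. The flow chart's ±4 days gives 23 to 31; the +4 days in protocol 5.2.6 gives 27 to 31.

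**5. Same-visit repeats.** SAP 10.1 always uses the repeat; 11.6.2 uses it only if sampled within the window. They differ only for an out-of-window repeat.

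**The case against.** **The by-visit design follows the protocol.** Section 9.3.1 asks for statistics at scheduled assessments and shift tables, which the SAP supplies, and 9.3 itself places the count in shift tables. This stands as far as it goes: by-visit tables are legitimate, and the protocol never specifies a worst post-baseline value or says that unscheduled results must count. A reader might infer that a worst-value shift including unscheduled tests is required; the text does not go that far. But a count of subjects with at least one abnormal value is most naturally an any-time count, and vital signs fail even the lenient reading.

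**Abnormal results reach subject-level tables by another route.** A reader might infer that safety signals vanish from the report. They do not. Clinically significant findings are to be recorded as adverse events (protocol 5.3.3, 5.3.5, 8.4.1). Values meeting AESI thresholds (protocol 8.2, to which SAP 11.6.1 refers) are counted per subject in the TEAE and AESI tables whatever the visit type. Among the repeat analytes this covers AST, ALT, bilirubin, lipase, troponin, CPK and NT-proBNP, 7 of 9, but not alkaline phosphatase or INR/prothrombin. What stays uncounted is abnormalities that are neither clinically significant nor over a threshold. AESIs are a separately listed secondary endpoint, so they do not formally replace the one on specific laboratory abnormalities.

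**LOCF may have been meant for efficacy only.** The SAP never says outright that it applies to safety laboratory data, and 11.6.2 does not mention imputation. It is therefore an inference from general wording that makes no exception. The measured repeat is left out of the summaries on either reading.

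**The data remain available.** All values are listed, and Table 14.3.3.5 allows a hand count for laboratory data. This is correct and lowers the severity.

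**Conclusion.** The point holds with limits. A protocol-required count is absent from the laboratory, vital-sign and ECG outputs and undeclared; a listed secondary endpoint has neither criteria nor output; and the mandatory repeat of a failed safety sample is excluded from Tables 14.3.3.1 to 14.3.3.4. These statements rest on the text alone.

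The numerical effect cannot be fixed. The documents give no sample-failure rate. The any-time bounds rest on an assumed pattern, and the 7.1% against 0.0% comparison on an assumed 14 subjects and one abnormal repeat. The carried-value ages apply only if LOCF covers laboratory data, and those at M27 and EoS depend on visit rules that the documents state in two ways and that must be reconciled.

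The primary endpoint, treatment-emergent adverse events, is unaffected. With purely descriptive analyses, full listings and the AE/AESI route, this lies between a minor point and one that should be fixed before database lock.

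**What to change.** - **Any-time counts.** Add n (%) of subjects with at least one post-baseline abnormal value for each laboratory parameter and for ECG, and state whether unscheduled results count. For vital signs, give it per parameter if the data allow. Otherwise give an overall count from the Review field in Listing 16.2.8.3 and declare that deviation in SAP 1.2.
- **Failed samples.** In SAP 11.6.2, assign a protocol 5.3.12 repeat to the scheduled visit whose sample failed and use it in Tables 14.3.3.1 to 14.3.3.4. Set a time limit, for example the 1-month limit the SAP already uses for endoscopy, and before the next scheduled visit. State in 10.4 that LOCF does not replace a measured repeat.
- **Repeat rules.** Align SAP 10.1 and 11.6.2 on out-of-window repeats.
- **Specific laboratory abnormalities.** Define and tabulate the endpoint, for which the AESI laboratory thresholds are a ready starting point, or declare its omission in SAP 1.2.

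The cost is SAP wording, one laboratory table (a second once the endpoint is defined), and one block each in Tables 14.3.4 and 14.3.6. Laboratory and ECG data are already collected. Whether vital-sign assessments exist per parameter must be checked, because the listing shows one Review field per visit. If unscheduled results are counted, subjects tested more often have more chances to be counted as abnormal, and a footnote should say so.
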